## 2.2 Overview of Proposed Study

Eligible patients must have had a prior objective response or a prolonged stable disease (6 months or more) to one prior anti-EGFR based therapy (either cetuximab or panitumumab) in combination with irinotecan (either irinotecan alone or irinotecan plus a fluoropyrimidine). Evidence of progressive disease must have been documented within 6 weeks from their last dose of anti-EGFR therapy. Patients should have been subsequently treated with one or more non-anti-EGFR containing regimens and should be at least 4-month-anti-EGFR-naïve before they can get enrolled on this proposed study. The schema for enrollment is summarized in the figure below.

Patients will be treated on the study with bi-weekly panitumumab in combination with FOLFIRI and the doses recommended by the NCCN guidelines for first or second line treatment. Since patients enrolled on this study are heavily pre-treated, the study will allow some flexibility in the irinotecan and 5-fluorouracil (5-FU) dosing as is detailed in section 5.2. Patients will continue on treatment until evidence of progressive disease or unacceptable toxicity. Response to treatment will be assessed with clinical imaging, which will be performed every 4 cycles (every 8 weeks).

This study will be conducted in compliance with the protocol, Good Clinical Practice (GCP) and the applicable legal and regulatory requirements.

### 3.0 PARTICIPANT ELIGIBILITY

---

#### 3.1 Eligibility Inclusion Criteria

Participant MRN:	Participant Initials: (L,F,M):
------------------	--------------------------------

Participants must meet the following criteria on screening examination to be eligible to participate in the study:

##### Informed consent

- \_\_\_ 1. Participant must have the ability to understand and the willingness to sign a written informed consent document.
- \_\_\_ 2. Participant must be willing to comply with study and/or follow-up procedures.

##### Age Criteria, Performance Status, and Life Expectancy

- \_\_\_ 3. Age: 18 years or older. The safety of the combination of FOLFIRI plus panitumumab has not been adequately assessed in patients younger than 18 years of age and therefore these patients are excluded from this study.
- \_\_\_ 4. ECOG Performance Status 0-2 (Appendix A).
- \_\_\_ 5. Life expectancy of  $\geq 3$  months.

##### Nature of Illness and Treatment History

- \_\_\_ 6. Histologically confirmed colon or rectal cancer with metastatic disease.
- \_\_\_ 7. Extended RAS and BRAF wild type status documented on archival tumor tissue or on fresh biopsy if no archival tissue present.
- \_\_\_ 8. Measurable disease defined by at least 1 lesion  $\geq 1$  cm.
- \_\_\_ 9. Documented objective response or stable disease lasting for 6 months or more to last prior anti-EGFR (cetuximab or panitumumab) in combination with irinotecan or FOLFIRI.
- \_\_\_ 10. Progression within 6 weeks following their last dose of anti-EGFR therapy.
- \_\_\_ 11. Treatment with a non-EGFR targeting regimen following progression on anti-EGFR plus irinotecan-based therapy.
- \_\_\_ 12. At least 4 months from prior anti-EGFR therapy prior to start of study treatment.
- \_\_\_ 13. At least three weeks from any non-anti-EGFR therapy prior to start of study treatment. Any number of prior therapies is permitted.
- \_\_\_ 14. Adequate recovery in the investigators opinion from any clinically significant toxicity from prior therapy.

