#### 11.1.1 Definitions

Evaluable for toxicity. All participants will be evaluable for toxicity from the time of their first treatment with FOLFIRI plus panitumumab.

Evaluable for objective response. Only those participants who have measurable disease present at baseline, have received at least one cycle of therapy, and have had their disease re-evaluated will be considered evaluable for response. These participants will have their response classified according to the definitions stated below.

Evaluable Non-Target Disease Response. Participants who have lesions present at baseline that are evaluable but do not meet the definitions of measurable disease, have received at least one cycle of therapy, and have had their disease re-evaluated will be considered evaluable for non-target disease. The response assessment is based on the presence, absence, or unequivocal progression of the lesions.

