#### Disease Parameters

Measurable disease. Measurable lesions are defined as those that can be accurately measured in at least one dimension (longest diameter to be recorded) as  $\geq 20$  mm by chest x-ray or as  $\geq 10$  mm with CT scan, MRI, or calipers by clinical exam. All tumor measurements must be recorded in millimeters (or decimal fractions of centimeters).

Malignant lymph nodes. To be considered pathologically enlarged and measurable, a lymph node must be  $\geq 15$  mm in short axis when assessed by CT scan (CT scan slice thickness recommended to be no greater than 5 mm). At baseline and in follow-up, only the short axis will be measured and followed.

Non-measurable disease. All other lesions (or sites of disease), including small lesions (longest diameter  $< 10$  mm or pathological lymph nodes with  $\geq 10$  to  $< 15$  mm short axis), are considered non-measurable disease. Bone lesions, leptomeningeal disease, ascites, pleural/pericardial effusions, lymphangitis cutis/pulmonitis, inflammatory breast disease, and abdominal masses (not followed by CT or MRI), are considered as non-measurable.

Note: Cystic lesions that meet the criteria for radiographically defined simple cysts should not be considered as malignant lesions (neither measurable nor non-measurable) since they are, by definition, simple cysts.

'Cystic lesions' thought to represent cystic metastases can be considered as measurable lesions, if they meet the definition of measurability described above. However, if non-cystic lesions are present in the same participant, these are preferred for selection as target lesions.

Target lesions. All measurable lesions up to a maximum of 2 lesions per organ and 5 lesions in total, representative of all involved organs, should be identified as **target lesions** and recorded and measured at baseline. Target lesions should be selected on the basis of their size (lesions with the longest diameter), be representative of all involved organs, but in addition should be those that lend themselves to reproducible repeated measurements. It may be the case that, on occasion, the largest lesion does

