#### 11.1.2 Methods for Evaluation of Measurable Disease

All measurements should be taken and recorded in metric notation using a ruler or calipers. All baseline evaluations should be performed as closely as possible to the beginning of treatment and never more than 4 weeks before the beginning of the treatment.

The same method of assessment and the same technique should be used to characterize each identified and reported lesion at baseline and during follow-up. Imaging-based evaluation is preferred to evaluation by clinical examination unless the lesion(s) being followed cannot be imaged but are assessable by clinical exam.

Clinical lesions Clinical lesions will only be considered measurable when they are superficial (*e.g.*, skin nodules and palpable lymph nodes) and  $\geq 10$  mm diameter as assessed using calipers (*e.g.*, skin nodules). In the case of skin lesions, documentation by color photography, including a ruler to estimate the size of the lesion, is recommended.

Chest x-ray Lesions on chest x-ray are acceptable as measurable lesions when they are clearly defined and surrounded by aerated lung. However, CT is preferable.

Conventional CT and MRI This guideline has defined measurability of lesions on CT scan based on the assumption that CT slice thickness is 5 mm or less. If CT scans have slice thickness greater than 5 mm, the minimum size for a measurable lesion should be twice the slice thickness. MRI is also acceptable in certain situations (*e.g.* for body scans).

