### 11.1.3 Response Criteria

#### 11.1.3.1 *Evaluation of Target Lesions*

Complete Response (CR): Disappearance of all target lesions. Any pathological lymph nodes (whether target or non-target) must have reduction in short axis to <10 mm.

Partial Response (PR): At least a 30% decrease in the sum of the diameters of target lesions, taking as reference the baseline sum diameters.

Progressive Disease (PD): At least a 20% increase in the sum of the diameters of target lesions, taking as reference the smallest sum on study (this includes the baseline sum if that is the smallest on study). In addition to the relative increase of 20%, the sum must also demonstrate an absolute increase of at least 5 mm. (Note: the appearance of one or more new lesions is also considered progressions).

Stable Disease (SD): Neither sufficient shrinkage to qualify for PR nor sufficient increase to qualify for PD, taking as reference the smallest sum diameters while on study.

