As a result, we will employ a modification of the Gehan 2-stage Phase II design. In the first stage, 14 participants will be accrued. Failure to observe a response if the true response is 20% or above would occur with a probability less than 5% (4.4%). Failure to observe at least 4 participants progression-free at the second evaluation (~4 months), would occur with less than 3% probability if the true 4-month PFS rate is 50%, and would occur with more than 95% probability if the true 4-month PFS rate was 10%, which is higher than placebo treatment 4-month PFS seen on the CORRECT trial.[1] As a result, if no objective responses are observed in 14 participants, and fewer than 4 participants are progression-free at the 4 month evaluation, the study will close for futility. If there is at least one response, or at least 4 participants progression-free at 4 months, an additional 11 participants will be accrued. The interim stopping for futility is such that there is a 46% chance of early stopping if the response rate is 5% and the 4-month PFS rate is 10%. This compares to 48.7% early stopping probability for the standard Gehan design if the true response rate is 5%, but allows us to pass the interim stopping condition if PFS suggests enough activity due to re-challenge to expand to a total of 25 participants.

With a total of 25 participants, the standard error of estimate for the response rate estimate and the 4-month PFS rate estimate will not exceed 10%.

All of the participants who met the eligibility criteria (with the exception of those who received no study medication) will be included in the main analyses of response and PFS, and all the secondary or correlative analysis described below.

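### Criterion 8 defines measurable disease by a 1 cm lesion alone, which conflicts with Section 11.1.1 and leaves some eligible patients without a target lesion and with an unclear place in the response denominator

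*Combined protocol and SAP*

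**What the plan says.** Section 3.1, criterion 8, asks for "Measurable disease defined by at least 1 lesion" of at least 1 cm. The synopsis repeats it. Neither place names a lesion type, an axis or an imaging method, and neither refers to Section 11 or RECIST.

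The Disease Parameters part of Section 11.1.1 uses 10 mm on CT or MRI for lesions in general, but adds restrictions:

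- For nodes: "To be considered pathologically enlarged and measurable, a lymph node must be" at least 15 mm in short axis. Nodes of at least 10 but under 15 "mm short axis), are considered non-measurable disease".
- "Bone lesions, leptomeningeal disease, ascites, pleural/pericardial effusions" and similar sites are non-measurable, with no size qualification.

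Target lesions are chosen from measurable lesions only. Section 11.1.3.1 defines partial response as "At least a 30% decrease in the sum of the diameters of target lesions". The Section 11.1.4 table for patients with only non-measurable disease has a complete response row but no partial response row.

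On who counts, Section 11.1.1 admits to the response-evaluable set "Only those participants who have measurable disease present at baseline, have received at least one cycle of therapy, and have had their disease re-evaluated". Section 13.1 instead puts "All of the participants who met the eligibility criteria" and received study medication into the main analyses of response and PFS. Sections 5.1 and 13.2 define an evaluable participant without mentioning measurable disease.

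**The concern.** Response rate is a primary endpoint alongside PFS. A patient whose only disease is a 12 mm short-axis node, or a 2 cm bone lesion, satisfies criterion 8 as worded, yet has nothing that Section 11 allows as a target lesion. The usual route to an objective response, partial response, is closed to that patient.

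The protocol then gives two answers on the denominator. Under Section 13.1 the patient stays in and can lower the estimated rate. Under Section 11.1.1 the patient drops out, and the estimate rests on fewer than 25. Because Sections 5.1 and 13.2 count the patient as evaluable, accrual would not be extended to replace the loss.

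**Working it through.** **Inputs.** Stage 1 n = 14, total n = 25, response rates of 20% and 5%, 4-month PFS rates of 50% and 10%, and a standard error limit of 10%, all from Section 13.1. The number k of patients with only Section 11 non-measurable disease is not in the documents, so k = 1 and k = 2 are assumptions.

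**1. The plan's own figures.**

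- P(0 responses in 14 at 20%) = 0.8^14 = 0.0440. Stated: 4.4%.
- P(fewer than 4 of 14 progression-free at 50%) = (1 + 14 + 91 + 364)/2^14 = 470/16384 = 0.0287. Stated: below 3%.
- Same event at 10% = 0.956. Stated: above 95%.
- 0.95^14 = 0.488, and 0.488 × 0.956 = 0.466 assuming independence. Stated: 48.7% and 46%.
- Worst-case SE at n = 25 = √(0.25/25) = 10.0%. Stated: not above 10%.

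All reproduce to within rounding or less than one percentage point. The problem is one of definition and involves no wrong figure.

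**2. Affected patients kept in the denominator (Section 13.1).** Suppose the rate is 20% among patients with measurable disease and zero among the k others. Zero is the extreme case.

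- k = 1: 0.20 × 24/25 = 19.2%
- k = 2: 0.20 × 23/25 = 18.4%

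The largest shift is 1.6 points. The SE at 20% is √(0.2 × 0.8/25) = 8.0 points.

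**3. Affected patients dropped (Section 11.1.1).** Worst-case SE:

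- n = 24: √(0.25/24) = 10.2%
- n = 23: √(0.25/23) = 10.4%

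At n = 25 the worst case sits exactly on the limit, so any loss exceeds it. This applies only to mid-range rates. With n = 24 the SE exceeds 10% when p(1 − p) > 0.24, that is, p between 40% and 60%. At p = 20% and n = 23 it is √(0.16/23) = 8.3%.

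**4. Stage 1.** Stopping needs no responses and also fewer than 4 of 14 progression-free at 4 months. At a 20% response rate among measurable patients and 50% PFS, assuming independence:

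- k = 0: 0.0440 × 0.0287 = 0.13%
- k = 2: 0.8^12 × 0.0287 = 0.0687 × 0.0287 = 0.20%

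Response and PFS are likely to be positively related, so independence is only a convenience. Whatever the dependence, the joint probability cannot exceed the PFS part alone, 2.9%, for any k.

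**The case against.** The strongest reply is that criterion 8 uses the term measurable disease, that Section 11 defines this term, and that the general CT/MRI threshold is the same 10 mm. On that reading only a cross-reference is missing. This holds for non-nodal soft-tissue lesions on thin-slice CT. It does not cover small nodes or bone, because criterion 8 supplies a competing definition in the checklist that has to be completed before registration.

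Three stronger readings are tempting, and the documents do not support them:

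- **That these patients cannot respond at all.** Section 11.1.3.2 and the non-measurable table allow complete response. For nodes this means short axis below 10 mm, with markers normalised if they were raised. A lone 12 mm node shrinking to 9 mm, a 25% reduction, would meet the size condition. Section 13.1 counts objective responses, so even the direction of the bias is not certain. The figures in step 2 are the zero-response extreme.
- **That one such patient breaks the plan's stage-1 bound of 5%.** With 13 measurable patients 0.8^13 = 5.5%, but the overall rate is then 0.20 × 13/14 = 18.6%. The plan's statement is conditional on a true rate of 20% or above, so it stays true.
- **That the chest x-ray and slice-thickness rules add materially to the conflict.** Section 11.1.2 does say "the minimum size for a measurable lesion should be twice the slice thickness" when slices exceed 5 mm, but it assumes slices of 5 mm or less. The study calendar specifies CT of chest, abdomen and pelvis, so the 20 mm x-ray threshold hardly applies.

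It is also fair to say that the denominator conflict is wider than criterion 8, because it arises for measurable patients who are never re-imaged. The eligibility edit alone would not settle it.

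**Conclusion.** The conflict is real. Criterion 8 and the synopsis admit patients whose only disease Section 11.1.1 calls non-measurable. Those patients cannot be scored as partial responses, and two sections disagree on whether they belong in the response analysis. The point rests on the text and does not depend on k.

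The expected numerical effect is modest: for one or two patients, at most 0.8 or 1.6 points on a 20% response rate, or a worst-case SE of 10.2% or 10.4%. These sizes assume the stated k and, for the first pair, no complete responses among the affected patients. The stage-1 calculations stand, and the change in the full stopping rule is negligible. The correction is worth making because it concerns the denominator of a primary endpoint and is cheap.

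**What to change.** Reword criterion 8 and the matching synopsis line to require at least one measurable lesion as defined in Section 11.1.1 (RECIST 1.1), which brings in the 15 mm short-axis rule for nodes and the exclusion of bone lesions.

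In the same amendment, reconcile Sections 11.1.1 and 13.1: name one denominator for the primary response rate, say how patients without a post-baseline assessment are counted in it, and label any other set as supportive.

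The cost is a few lines of text. The downside is that a few patients with only small nodal or bone disease become ineligible, although they could have contributed to PFS and possibly to complete responses. If the sponsor prefers to keep them, the protocol should say so openly and state how they count towards response.

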##### Clinical Labs for Assessing Adequate Organ Function

- \_\_\_ 15. Absolute neutrophil count (ANC)  $\geq 1.5 \times 10^9/L$
- \_\_\_ 16. Hemoglobin (Hgb)  $\geq 9$  g/dL without transfusions

- \_\_\_ 17. Platelets (PLT)  $\geq 100 \times 10^9/L$  without transfusions
- \_\_\_ 18. AST (SGOT) and/or ALT (SGPT)  $\leq 2.5 \times$  upper limit of normal (ULN); patient with liver metastases  $\leq 5 \times$ ULN
- \_\_\_ 19. Total bilirubin  $\leq$  ULN
- \_\_\_ 20. Creatinine  $\leq 1.5$  mg/dL
- \_\_\_ 21. Magnesium  $\geq 1.2$ mg/dL or 0.5 mmol/L
- \_\_\_ 22. Negative serum  $\beta$ -HCG test (female patient of childbearing potential only), to be performed locally within the screening period.

#### Child Bearing Potential

- \_\_\_ 23. Agreement by females of childbearing potential **and** sexually active males to use an effective method of contraception (hormonal or barrier method of birth control or abstinence) prior to study entry and for three months following duration of study participation. The effects of study treatment on a developing fetus have the potential for teratogenic or abortifacient effects. Should a woman become pregnant or suspect that she is pregnant while participating on the trial, she should inform her treating physician immediately.

### **3.2 Eligibility Exclusion Criteria**

Prospective participants who meet any of the following criteria will not be eligible for admission into the study:

#### History to Previous therapies

- \_\_\_ 1. History of severe anti-EGFR toxicity requiring drug discontinuation or dose-modification within the first 4 months of prior anti-EGFR therapy
- \_\_\_ 2. History of intolerance to irinotecan at dose-intensity of 125 mg/m^2/2 weeks or lower
- \_\_\_ 3. History of intolerance to 5-FU at dose-intensity of 1800 mg/m^2/2 weeks or lower

#### Concomitant medications

- \_\_\_ 4. Current use (or planned use during the treatment period) of other investigational agents, or biological, chemotherapy, radiation or other anti-tumor therapy. See Inclusion Criteria 12 & 13, for required washout periods from these therapies.
- \_\_\_ 5. Co-medication that may interfere with study results; e.g. immuno-suppressive agents other than corticosteroids, such as systemic cyclosporine and tacrolimus. Consult Principal Investigator for questions, including necessary washout period for the specific drug.
- \_\_\_ 6. No St John's wort supplement or other herbal supplementation is allowed while on trial. Patients are not to take grapefruit juice during study treatment as these may alter the metabolism of irinotecan.
- \_\_\_ 7. Use of drugs known to **inhibit** UGT1A1, such as Atazanavir, Gemfibrozil, Indinavir, or Ketoconazole while on study treatment. (Patients using these drugs must not take these drugs on the day study treatment begins and for the duration of study treatment).

- \_\_\_ 8. Planned use of **strong CYP3A4 inhibitors** or **CYP3A4 inducers** (See Table 5.6) while on study treatment unless deemed clinically necessary with no reasonable alternatives and with expressed permission from the principal investigator.
- \_\_\_ 9. If on anticoagulation, participant must be on stable therapeutic dose prior to enrollment.

#### Other illnesses or conditions

- \_\_\_ 10. Impairment of gastrointestinal function or gastrointestinal disease (e.g., active ulcerative disease, uncontrolled nausea, vomiting, diarrhea, malabsorption syndrome, extensive small bowel resection)
- \_\_\_ 11. Major surgery  $\leq$  3 weeks prior to starting study drug or who have not recovered from side effects of such procedure.
- \_\_\_ 12. Unstable pulmonary embolism, deep vein thrombosis, or other significant arterial/venous thromboembolic event  $\leq$  30 days before enrollment.
- \_\_\_ 13. Clinically significant cardiovascular disease (including myocardial infarction, unstable angina, symptomatic congestive heart failure, serious uncontrolled cardiac arrhythmia)  $\leq$  6 months prior to enrollment
- \_\_\_ 14. History of interstitial lung disease (ILD) eg, interstitial pneumonitis, pulmonary fibrosis or evidence of ILD on baseline chest CT or MRI
- \_\_\_ 15. Other active malignancies except cervical carcinomas in situ or clinically insignificant non-melanoma skin cancers.
- \_\_\_ 16. Clinically significant uncontrolled illness or active infections.
- \_\_\_ 17. History of allergic reactions attributed to compounds of similar chemical or biologic composition to irinotecan, 5-FU, leucovorin or any of the products to be administered during dosing.
- \_\_\_ 18. Pregnant women and women who are lactating. FOLFIRI plus panitumumab are agents with the potential for teratogenic or abortifacient effects. Because there is an unknown but potential risk for adverse events in nursing infants secondary to treatment of the mother with the administered chemotherapy, breastfeeding should be discontinued if the mother is enrolled on this study.
- \_\_\_ 19. Any other condition that would, in the Investigator's judgment, contraindicate the patient's participation in the clinical study due to safety concerns or compliance with clinical study procedures, e.g., infection/inflammation, intestinal obstruction, unable to swallow medication, social/ psychological issues, etc.

